3.1.7.2 Missing Primary Efficacy Endpoints

For continuous endpoints, where applicable, the last observation carried forward (LOCF) method will be used for missing data, where the patient’s last non-missing value (including baseline) will be used to impute the missing value if a patient is lost to follow-up. For the interim analysis, if there are patients who missed V8 (Day 168) but have V9 (Day 196) or V10 (Day 224) efficacy data, then V9 (Day 196) or V10 (Day 224) data, whichever were obtained earlier, will be used to fill in the gap. For the 12-month analysis, the LOCF method will be used in the descriptive analyses (see Section 3.1.7.3 for intercurrent event handling due to site restriction).

In calculating HFMSE and RHS, if 20% or fewer items are missing, then these items will be imputed to be 0 (unable) when summing all 33 items. If greater than 6 items are missing, then the total score will be set to be missing.

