9.1.1. Efficacy Parameters

9.1.1.1. Revised Hammersmith Scale

The RHS will be performed for the ambulatory patient subgroup (Cohort 1). Administration of the RHS includes the timed rise from floor and 10-Meter Walk/Run tests. The RHS is a 36-item clinical assessment for physical abilities of patients with Type 2 SMA, and ambulatory and nonambulatory patients with Type 3 SMA. The RHS includes 33 items that are graded on a scale of 0, 1, 2, where 0 denotes the lowest level of ability/function and 2 denotes the highest level of ability ([Ramsey 2017](#)). The remaining 3 items are scored 0, 1, where 0 denotes an inability and 1 denotes an ability to achieve. The maximum achievable score is 69.

9.1.1.2. 10-Meter Walk/Run

The 10-Meter Walk/Run test is an enhanced function of the RHS used for ambulant patients with Type 3 SMA. It is a measure of the time taken to walk/run 10 meters.

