2.3 Study Endpoints

2.3.1 Efficacy Endpoints

The efficacy endpoints for each cohort are outlined in Table 6. Functional outcome measures (e.g., HFMSE/Revised Hammersmith Scale [RHS], 6-minute Walk Test [6MWT], World Health Organization [WHO] Motor Milestones, Revised Upper Limb Module [RULM], 30-Second Sit-to-Stand, Endurance Shuttle Nine Hole Peg Test [ESNHPT], or Endurance Shuttle Box and Block Test [ESBBT]) will be conducted and assessed by the Physical Therapist. Requirements for the order of assessments, duration of assessments and rest periods between assessments will be outlined in a separate Physical Therapist training manual. Similarly, total score from each assessment should there be any missing values will be determined per the instrument tool scoring algorithm for these cases.

Study procedures will not be conducted for patients who develop an AE (e.g., musculoskeletal injury) during the study, irrespective of relatedness to study drug, that the Investigator considers would make it unsafe to perform a functional outcome assessment. Upon resolution of the AE, and if the Investigator assesses it would be safe to do so, performance of that study procedure will be resumed at the next scheduled assessment as indicated in Table 3, Table 4, and Table 5.

Table 6: Efficacy Endpoints by Cohort

	Cohort 1	Cohorts 2 and 3
Primary:	Change from Baseline in the RHS total score at Day 364 (V15)	Change from Baseline in the HFMSE total score at Day 364 (V15)
Secondary:	
 • Change from Baseline in the RHS total score at other prespecified timepoints • Proportion of patients achieving various magnitudes of change in RHS score from Baseline • Change from Baseline in the 6MWT • Change from Baseline in the 30- Second Sit-to-Stand • Change from Baseline in the 10-meter Walk/Run (from the RHS) • Change from Baseline in the time to rise from floor (from the RHS) 	
 • Change from Baseline in the HFMSE total score at other prespecified timepoints • Proportion of patients achieving various magnitudes of change in HFMSE score from Baseline • Change from Baseline in the RULM total score • Proportion of patients achieving various magnitudes of change in RULM from Baseline • Change from Baseline in the number of WHO motor development milestones attained • Proportion of patients who attain a new WHO motor development milestone relative to Baseline

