2.3.1.1 Revised Hammersmith Scale (RHS)

The RHS will be performed for the ambulatory patient subgroup (Cohort 1). Administration of the RHS includes the timed rise from floor and 10-meter Walk/Run tests. The RHS is a 36-item clinical assessment for physical abilities of patients with Type 2 SMA, and ambulatory and nonambulatory patients with Type 3 SMA. The RHS includes 33 items that are graded on a scale of 0, 1, 2, where 0 denotes the lowest level of ability/function and 2 denotes the highest level of ability (Ramsey 2017). The remaining 3 items are scored 0, 1, where 0 denotes an inability and 1 denotes an ability to achieve. The RHS is calculated by the sum of the 36 items and achievable score range is [0, 69].

The RHS for SMA is based on the original HFMSE. Differences are seen on page 44 of the [RHS manual](#). RHS is used for Cohort 1, as it is appropriate for the SMA Type 3 ambulatory patients. Based on the decline in placebo patients in the HFMSE scale by Day 364 in a previous trial across similar cohort groups to this study (e.g., Darras 2019), any population mean increase above baseline would be clinically relevant for either RHS or HFMSE. Additional analyses will be performed on a patient level with success defined as any patient with a change from Baseline of 3 or more at V15 (Day 364). The figure below is an excerpt from Figure 1 in the RHS manual (SMA REACH UK, 2015):

Figure 4: How the RHS Fits in the Continuum of Outcome Measures in RHS

2.3.1.2 10-meter Walk/Run

The 10-meter Walk/Run test is an enhanced function of the RHS used for ambulant patients with Type 3 SMA. It is a measure of the time taken to walk/run 10 meters.

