2.3.1.6 Hammersmith Functional Motor Scale Expanded (HFMSE)

The HFMSE assesses the physical abilities of patients with Type 2 and Type 3 SMA (O'Hagen 2007; Glanzman 2011) and will be performed for nonambulatory patient subgroups (Cohorts 2 and 3). It consists of 33 items graded on a scale of 0, 1, 2, where 0 denotes unable, 1 denotes performed with modification or adaption, and 2 denotes without modification or adaptation. The HFMSE total score is the sum of all the 33 items and the maximum score is 66.

In conducting the HFMSE test, Question 3 reported the score for both hands. The higher score will be used in calculating the total score.

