3.4.1 Cohort 1: High Dose

3.4.1.1 Primary Efficacy Endpoint

The primary efficacy endpoint is the change from Baseline at V15 (Day 364) in RHS total score. Summary statistics will be generated along with the 95% CI based on the Student's t-distribution for the change from Baseline.

The cohort will be analyzed as total and by patients who received SRK-015 as monotherapy and in addition to a SMN upregulator therapy.

A waterfall plot of unit changes from baseline in functional scores will be displayed for each post-baseline visit.

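### The SAP's missing-item rule for HFMSE and RHS uses numbers that fit only the 33-item HFMSE; for the 36-item RHS the item count is wrong and the rule contradicts itself at exactly 7 missing items

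*Combined protocol and SAP*

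**What the plan says.** SAP 3.1.7.2 opens its item-level rule by naming both the HFMSE and the RHS, and then says: "if 20% or fewer items are missing, then these items will be imputed to be 0 (unable) when summing all 33 items". The sentence after it reads: "If greater than 6 items are missing, then the total score will be set to be missing". No separate numbers are given for the RHS.

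The scales are defined elsewhere:

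- **HFMSE**, SAP 2.3.1.6: "The HFMSE total score is the sum of all the 33 items and the maximum score is 66".
- **RHS**, SAP 2.3.1.1: "The RHS is calculated by the sum of the 36 items and achievable score range is [0, 69", that is, 0 to 69. The same section says "The RHS includes 33 items that are graded on a scale of 0, 1, 2" and that the other 3 items are scored 0 or 1. Protocol 9.1.1.1 agrees: "The maximum achievable score is 69".

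The RHS total is Cohort 1's primary measure (SAP 3.4.1.1): "The primary efficacy endpoint is the change from Baseline at V15 (Day 364) in RHS total score".

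SAP 2.3.1 has one more general sentence on missing values: "total score from each assessment should there be any missing values will be determined per the instrument tool scoring algorithm for these cases". SAP Section 6, which lists departures from the protocol's statistics, does not touch the point.

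**The concern.** A derivation rule for a primary endpoint should give one answer for every possible input. For the RHS this one does not, in two respects.

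1. The number of items to be summed disagrees with the definition of the scale. The slip is easy to misread, because 33 is also the number of RHS items scored 0 to 2.
2. A percentage limit and an absolute limit are both stated. They coincide for a 33-item scale but not for a 36-item scale.

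At stake are the mean change in RHS, its 95% confidence interval, and the patient-level success count (a change of 3 or more at Day 364, SAP 2.3.1.1). In a cohort of 20, and in background-therapy subgroups of about 10, one patient's total is visible in each of these.

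**Working it through.** **Inputs.** Imputation limit 20% and voiding limit of more than 6 items (SAP 3.1.7.2). HFMSE 33 items, maximum 66 (SAP 2.3.1.6). RHS 36 items, 33 scored 0–2 and 3 scored 0–1, range 0–69 (SAP 2.3.1.1; Protocol 9.1.1.1). Cohort 1 planned at N=20, about 10 of them without an approved SMA treatment (SAP 2.2.1).

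**Step 1: the plan's own figures.** The largest number k of missing items with k/n ≤ 0.20, for n = 33: 0.20 × 33 = 6.6, so k = 6. The total is voided from 7 upward, which is the stated cut-off. The rule reproduces for the HFMSE.

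**Step 2: the same rule for the RHS.** 0.20 × 36 = 7.2, so k = 7. The cut-off of more than 6 still voids the total from 7 upward.

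| Missing items | HFMSE share (n=33) | HFMSE result | RHS share (n=36) | RHS, first sentence | RHS, second sentence |
|---|---|---|---|---|---|
| 6 | 18.2% | impute 0 | 16.7% | impute 0 | not voided |
| 7 | 21.2% | missing | 19.4% | **impute 0** | **missing** |
| 8 | 24.2% | missing | 22.2% | no imputation | missing |

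The conflict is at 7 RHS items and nowhere else. The HFMSE has neither a conflict nor a gap.

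**Step 3: the item count.** The full RHS maximum is 33 × 2 + 3 × 1 = 69, as both documents state. The 33 items scored 0–2 reach only 33 × 2 = 66. So the 33 in SAP 3.1.7.2 cannot be reconciled with the RHS by taking it to mean those items.

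**Step 4: size if one such total occurs at Day 364.** Let c be the patient's true change, m the mean change of the other 19, and a the average score that the 7 unassessed items would have had. Imputing zeros gives the patient c − 7a. If the total is set to missing, either an earlier change L is carried forward or the patient is left out. The difference in the cohort mean is then:

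- carried forward: [(19m + L) − (19m + c − 7a)]/20 = (L − c + 7a)/20
- left out: m − (19m + c − 7a)/20 = (m − c + 7a)/20

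Assume L = c, or m = c, respectively. Both then reduce to 7a/20. The value of a is not in the documents, so a range is shown:

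| Assumed a | Shift in patient's change (7a) | Shift in mean, n=20 | Shift in mean, subgroup of 10 |
|---|---|---|---|
| 0.5 | 3.5 | 0.175 | 0.35 |
| 1 | 7 | 0.35 | 0.70 |
| 2 | 14 | 0.70 | 1.40 |

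The last row needs all seven items to be two-point items that would have scored the maximum. These figures say what happens if a case occurs. They are not expected effects.

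**The case against.** The strongest reply is that this is a copying slip of almost no consequence. SAP 2.3.1.1, which defines the RHS total, already directs summing 36 items, and a program following it is unaffected by the wrong count. The cut-off conflict needs exactly 7 missing items on one scale in one cohort. SAP 3.1.5 plans no formal testing, so no decision hangs on it. Detailed derivation specifications are kept in stand-alone documents (SAP Section 7) and may already be right. The 12-month database lock is dated 19 January 2021 (Protocol 6.2), so for the primary analysis the correction may amount to documentation.

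Most of that stands, and it limits what may be inferred. Four stronger readings are tempting but not supported:

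- **That RHS totals in general lose the three 0/1 items, up to 3 points per patient.** The wording occurs only in the missing-item rule, and the definition of the scale contradicts it. Misprogramming is possible but not shown.
- **That SAP 2.3.1 and SAP 3.1.7.2 contradict each other.** The instrument's algorithm is not reproduced and may agree. Reading the specific rule as governing the general sentence is natural. At most a cross-reference is wanted.
- **That the shift is a stated share of the confidence interval.** The documents give no SD for the RHS change (2.5 is given for the HFMSE only). A patient displaced by 7 points would also widen the interval, so a ratio to a fixed half-width would overstate the effect.
- **That zero-imputation is itself the error.** That is a separate question, which would apply equally to the HFMSE, where the rule is consistent.

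The reply does not remove the defect: a sentence that names the RHS gives the wrong item count, and at 7 missing items its two limits cannot both be followed.

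**Conclusion.** The point holds in a narrow form. For the RHS, SAP 3.1.7.2 is wrong on the item count (33 against 36) and self-contradictory at exactly 7 missing items. For the HFMSE it is sound. Only Cohort 1's descriptive results can be affected. The illustrative size is about 7 points for one patient and about 0.35 in the mean at n=20. It assumes one such total at Day 364, an average of 1 point on the unassessed items, and an alternative handling that recovers the patient's true change. The documents give no rate of missing items. If no RHS form has exactly 7 missing and the program sums 36 items, the results do not change. The case for correcting it is that a primary-endpoint derivation should be unambiguous and that the correction is nearly free, not that the results are known to be distorted.

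**What to change.** Replace the shared rule in SAP 3.1.7.2 with one rule per scale:

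- **HFMSE:** sum 33 items; up to 6 missing items are imputed as 0; with 7 or more missing, the total is missing.
- **RHS:** sum 36 items (33 scored 0–2, 3 scored 0–1), with one cut-off. Either impute 0 for up to 7 missing and set the total to missing at 8 or more, which follows the 20% limit, or keep the present cut-off of more than 6 and drop the 20% wording for this scale (6/36 = 16.7%). Both are coherent, but only one should be stated.

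A short cross-reference saying how this section relates to the general sentence in SAP 2.3.1 would be a courtesy to the programmer.

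The cost is about two sentences and a check of the RHS derivation program; no new data are needed. The SAP's date is not visible. If the change comes after the 12-month lock, SAP Section 1 sends it to the clinical study report, where it should be recorded as a clarification. It also remains useful later, since SAP 3.1 applies the 12-month method to the Extension Periods.

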2.3.1.7 Revised Upper Limb Module (RULM)

The RULM is a 20-item assessment of upper limb function in nonambulatory SMA patients (young children as well as adults) (Mazzone 2017). The 19 scored items test functions that relate to everyday life, such as bringing hands from lap to table, pressing a button, and picking up a token. The items are scored 0, 1, 2, where 0 denotes unable, 1 denotes able with modification, and 2 denotes able with no difficulty. The RULM is calculated by the sum of the 19 items. The maximum score achievable is 37 (since one item only has possible values of 0 or 1). Responses marked as ‘Could Not Test’ (CNT) will be considered the same as 0 when determining the total score. Non-ambulant patient subgroups (Cohorts 2 and 3) will perform the RULM. The RULM will be completed by patients who are 30 months of age or older at the time of the baseline assessment.

To calculate RULM, where scores for both hands were collected, but only one score is needed, the higher of the two scores will be used to calculate the total score.

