3.1.3 Definition of Baseline

Baseline for all efficacy and safety variables will be defined as the last measurement prior to the first dose of study drug.

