3.4.3.3 Tertiary Efficacy Analyses

The following tertiary endpoints will be analyzed for Cohort 3:

- Change from Baseline in Time to limitation on ESNHPT or ESBBT to V15 (Day 364), V8 (Day 168) and all other scheduled visits
- Change from Baseline in PEDI-CAT to V15 (Day 364), V8 (Day 168) and all other scheduled visits
- Change from Baseline in PROMIS Fatigue Questionnaire to V15 (Day 364), V8 (Day 168) and all other scheduled visits and
- Time to therapeutic effect as compared between low and high dose SRK-015 arms to V15 (Day 364), V8 (Day 168) and all other scheduled visits.

The same analysis method as the secondary efficacy analysis in Cohort 3 will be used for all tertiary endpoints except the time to therapeutic effect, as compared between low and high dose SRK-015 arms. The time to therapeutic effect will be assessed using Kaplan-Meier life tables. The following therapeutic effects will be examined separately: improvement of at least 3.0 points from Baseline in HFMSE total score, and improvement of at least 2.0 points from Baseline in RULM score.

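### Untested motor items are scored 0 at Baseline as well as later, so a gap on Day 0 can show up as a gain at every later visit

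*Combined protocol and SAP*

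**What the plan says.** - **HFMSE and RHS items (SAP 3.1.7.2):** "if 20% or fewer items are missing, then these items will be imputed to be 0 (unable", the total for either scale being taken over 33 items. The next sentence sets the limit: "If greater than 6 items are missing, then the total score will be set to be missing".
- **RULM items (SAP 2.3.1.7):** responses marked CNT "will be considered the same as 0 when determining the total score". There is no limit on how many.
- **Baseline (SAP 3.1.3):** "Baseline for all efficacy and safety variables will be defined as the last measurement prior to the first dose of study drug". It need not be item-complete, and there is no fallback to an earlier item score.
- **Missing values in general (SAP 2.3.1):** "total score from each assessment should there be any missing values will be determined per the instrument tool scoring algorithm". Nothing says how this relates to the two rules above.
- **Where the totals are used:** change from Baseline at Day 364 in RHS or HFMSE is the primary endpoint (SAP Table 6). SAP 2.3.1.1 defines patient-level success as a change of 3 or more. SAP 3.4.3.3 defines therapeutic effect in Cohort 3 as 3 HFMSE points or, separately, "improvement of at least 2.0 points from Baseline in RULM score".
- **Schedule (SAP Table 3):** the motor measures are done both at Screening, at least 7 days before the first infusion, and on Day 0.
- **Sensitivity analyses (SAP 3.2.1 and 3.4):** these restore assessments made after missed doses and use the PP Population. Neither varies the item rule.

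**The concern.** On the HFMSE and RULM a 0 is a finding: the patient is unable. On the RHS it is the lowest level of function. An item that was not tested does not by itself show either. Scoring it 0 at a follow-up visit pulls the change down, which is cautious in a study looking for improvement. Scoring it 0 at Baseline pushes the change up, and one understated Baseline total feeds every later change score, waterfall plot and responder count. A later gap affects only the visit where it occurs. In the Kaplan-Meier analysis of time to effect, a false gain can count as an event at the first assessment, and SAP 3.4.3.3 asks for no confirmation.

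The design offers little protection. Cohorts 1 and 2 have no control arm, and the primary endpoint in Cohort 3 is the within-arm change on high dose (SAP 3.4.3.1). SAP 2.3.1.1 treats any mean increase above Baseline as clinically relevant, so even a small artefact would be read as signal.

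**Working it through.** **1. The plan's own figures.** For the HFMSE, 0.20 × 33 = 6.6, so at most 6 items can be zero-filled, which agrees with the cut-off of 6. The RHS has 36 items (SAP 2.3.1.1): 0.20 × 36 = 7.2, and 7/36 = 19.4%. Seven missing RHS items are therefore imputed under the first sentence and set to missing under the second, so the RHS cap is only roughly 6.

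The effect sizes in SAP Table 1 (0.66 at n = 20, 0.778 at n = 15) give power of 0.799 and 0.800 with a noncentral t calculation. At the plan's SD of 2.5 they are 1.65 and 1.95 HFMSE points, stated as 1.7 and 2.

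**2. What the rule does to one item.** Let *b* be the score the patient would have had on Day 0 and *f* the score at a later visit.

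- Untested at Baseline, tested later: recorded change = *f* − 0 = (*f* − *b*) + *b*. The artefact is +*b*.
- Tested at Baseline, untested later: recorded change = 0 − *b* = (*f* − *b*) − *f*. The artefact is −*f*.
- If the item was untested because of true inability, *b* = 0 and there is no artefact.

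The net bias is the sum of *b* over Baseline gaps minus the sum of *f* over later gaps.

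**3. Against the patient-level thresholds, with no true change (*b* = *f*).**

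| Baseline gap | Recorded change | Threshold |
|---|---|---|
| One RULM item worth 2 | +2 | 2: met |
| Two HFMSE or RHS items worth 2 and 1 | +3 | 3: met |
| Two HFMSE or RHS items worth 2 each | +4 | 3: met |
| Six HFMSE items worth 2 each (maximum) | +12 | 3: met |

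**4. Effect of one such patient on the mean.** Shift = points ÷ n.

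| Points in one patient | n = 10 | n = 15 | n = 20 |
|---|---|---|---|
| 2 | 0.20 | 0.13 | 0.10 |
| 12 | 1.2 | 0.8 | 0.6 |

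The detectable effects in step 1 belong to n = 15 and n = 20. The plan gives no one-arm figure for n = 10.

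**5. Illustration across a cohort.** The documents give no rate of untested items, so the affected share is assumed. Also assumed: true mean change 0, SD 2.5, Baseline gaps only, each item worth 2. Mean bias = points × share. The other columns come from 50,000 simulated cohorts per row and sample size.

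| Share, items each | Mean bias | 95% CI wholly above 0, n = 15 | Same, n = 20 | Patients at ≥ 3 points |
|---|---|---|---|---|
| None | 0 | 2.5% | 2.5% | 11.5% |
| 5%, one | 0.10 | 3.3% | 3.6% | 12.7% |
| 10%, one | 0.20 | 4.6% | 5.1% | 13.8% |
| 20%, one | 0.40 | 7.5% | 9.2% | 16.1% |
| 20%, two | 0.80 | 15% | 19% | 22.3% |

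These rows show one direction only. Gaps after Baseline would offset them.

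**The case against.** The best reply is that the rule is symmetric and that the documents point to fewer gaps at Baseline than later. Inclusion criterion 12 requires that no physical limitation prevents the motor measures. Exclusion criteria 3, 4 and 6 remove recent acute illness, unstable contractures and recent limiting surgery. Protocol 7.4 lets an acute condition delay the Baseline visit. Testing may be spread over the 96 hours before dosing, and a therapist manual sets the order and rest periods. Nothing comparable protects Day 364, where a zero works against the drug. In Cohort 3 the same rule applies to both randomised arms, so the dose comparison is not systematically biased. All analyses are descriptive (SAP 3.1.5), and the RULM endpoints are secondary or tertiary. All of this stands. It bears on how often and how much, and leaves the Baseline mechanism in place.

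Some stronger readings are tempting, and the documents do not support them.

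- **That the rule biases the trial towards the drug.** This would need Baseline gaps, weighted by score, to outweigh later ones. There are no data on either.
- **That SAP 2.3.1 contradicts SAP 3.1.7.2.** The instruments' algorithms are not in the documents. If they score untested items 0, the passages agree. What is missing is a statement of which governs.
- **That every zero for an untested item is wrong.** CNT is not defined beyond its name. Where it reflects true inability, 0 is correct and a later gain is real.
- **That the adverse-event text in SAP 2.3.1 produces item-level zeros.** It concerns omitting an assessment that would be unsafe, in which case there is no total to fill.

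**Conclusion.** The point holds for Baseline. As written, the zero rules apply to the last pre-dose measurement, and an item that was untested then but could have been scored adds its own score, up to 2 points, to the change at each later visit where it is tested. One item can meet the RULM threshold and two can meet the HFMSE or RHS threshold. One patient at the HFMSE maximum of 12 points would move a cohort mean by 0.6 to 1.2, but that needs six untested items all worth 2 and is an upper bound.

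That the rules reach Baseline is inferred from the absence of any visit restriction; the SAP does not say so in words. Net size and direction across the trial are unknown. This is a worthwhile, inexpensive improvement to the scoring rule, and it gives no ground for saying that the results are inflated.

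**What to change.** In SAP 3.1.7.2 and 2.3.1.7, for HFMSE, RHS and RULM:

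1. When an item is missing or CNT on Day 0, use that item's Screening score if it was tested then.
2. Keep the zero rule after Baseline as the main analysis. Carrying item scores forward after Baseline would be a poor substitute: in a progressive disease it could preserve abilities since lost, and so replace a conservative rule with one that may favour the drug.
3. Add a sensitivity analysis that computes change only on items tested at both visits. This removes the artefact in both directions.
4. State in SAP 2.3.1 whether 3.1.7.2 and 2.3.1.7 or the instrument's scoring algorithm governs. At the same edit, correct the reference to 33 items so that the RHS cap is unambiguous.

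The cost is a small extra derivation, with no new data, because the battery is already scheduled at Screening. The assumption is that the item did not change between Screening and Day 0: normally 7 to 28 days, and up to 28 + 14 = 42 where Protocol 7.4 allows a delay. Protocol 6.2 records that the 12-month database is locked, so any change to that analysis should be labelled as made after lock. The extension analyses reuse the same method (SAP 3.1) and can adopt the rule prospectively.
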